## 8. Efficacy Analyses

All imaging will be assessed by both investigators and a blinded central radiography review vendor, according to Response Evaluation Criteria In Solid Tumors version 1.1 (RECIST 1.1). The blinded central review disease response assessments will be used as the primary measure for the efficacy endpoints, and the investigator disease assessments will be used as supportive measures for these analyses. All the disease assessments from the randomization until the clinical cutoff date or the end of study will be used in the deviation of the secondary efficacy endpoints, unless otherwise specified.

[figure not shown]

For all the time-to-event endpoints described in this section, the time interval will be reported in unit of week.

### 8.1. Primary Efficacy Endpoint

The overall survival (OS) is defined as the time from the randomization to the death due to any cause. Patients who have not died by the time of data cutoff or study end will be censored at the last known alive date, or the data cutoff date for final analysis if the last known alive date is not available yet.

OS time will be calculated as Date of death (or date of last known alive/cutoff date) minus Randomization date + 1.

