6.4.13. Phase 2 and Phase 2 Extension End of Treatment (EoT) Visit

When progressive disease or withdrawal from study has been confirmed, the EoT visit will be conducted at least 28 Days (+/- 7) after last dose of study medication. An optional post-progression tumor biopsy sample will be requested from patients and may be provided at any time post progression. EoT visit procedures should be performed in the following order:

- Weight, and vital signs (blood pressure, temperature and heart rate);
- Blood sample for hematology and serum chemistry;
- Blood sample for humoral and cellular immunology;
- Blood sample for exploratory endpoints;
- Urine pregnancy test (female);
- Physical examination;
- ECOG performance score;
- Cardiac assessment by echocardiography or MUGA scan and 12-lead ECG;
- Record concomitant treatments;
- Record adverse events (AEs to be checked at least 28 days after last study treatment per [Section 9.2: Reporting Period](#)).

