6.4.14. Phase 2 Post-Treatment Follow-up Visit (Every 42 days after EoT visit)

This visit may be conducted via phone, email, review of medical records or via publicly available information. A visit window of +/- 7 days is allowable.

- Radiographic assessment (only for patients who withdrew from study before progressive disease was confirmed);
- Record survival follow-up assessment;
- Record post-study anti-cancer treatment.

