6.5.3. Additional Discontinuation Criteria

Patients must discontinue from the study if any of the following additional criteria are met:

- The patient requests discontinuation from the study;
- The Sponsor stops the study;
- The Sponsor stops the patient's participation in the study;
- The patient becomes pregnant during the study period.

Investigational Product: IMU-131
Protocol Identifier: IMU.ACS.001
Protocol Version: Protocol Global Amendment #5, 27 September 2023

Patients may withdraw from the study at any time at their own request, or they may be withdrawn at any time at the discretion of the investigator or Sponsor for safety or behavioral reasons, or the inability of the patient to comply with the protocol required schedule of study visits or procedures at a given study site.

If a patient does not return for a scheduled visit, every effort should be made to contact the patient. In any circumstance, every effort should be made to document patient outcome, if possible. The investigator should inquire about the reason for withdrawal, request the patient to return for a final visit, if applicable, and follow-up with the patient regarding any unresolved adverse events (AEs).

If the patient withdraws from the study, and also withdraws consent for disclosure of future information, no further evaluations should be performed, and no additional data should be collected. The Sponsor may retain and continue to use any data collected before such withdrawal of consent.

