#### Treatment Period

Patient who are determined to be eligible for the study will be randomized on the Baseline/Day 0 visit. Treatment for both groups will begin at the Baseline/Day 0 visit.

Patients in the IMU-131 plus chemotherapy group will receive vaccination of IMU-131 at Baseline/Day 0, Day 14, Day 35, Day 77, Day 140 and then every 63 days until disease progression. Patients in both the IMU-131 plus chemotherapy group and the chemotherapy alone group will receive chemotherapy starting at the Baseline/Day 0 visit and then every 21 days for a maximum of 6 cycles as clinically indicated or until disease progression, whichever occurs sooner. Chemotherapy will be consisting of:

- Cisplatin by intravenous administration at 80 mg/m^2 on the first day of each cycle and either 5-FU, 4000 mg/m^2 CIV (administered as 1000 mg/m^2/day as continuous infusion for 96 hours on days 1 to 4 of each cycle) or capecitabine for 14 days at 2000 mg/m^2/day, orally (administered as 1000 mg/m^2 twice daily morning and evening for a total of 2000 mg/m^2/day on days 1 to 14 of each cycle);
- Or oxaliplatin, by intravenous administration at 130 mg/m^2 on Day 1 of each cycle and capecitabine for 14 days at 2000 mg/m^2/day, orally (administered as 1000 mg/m^2 twice daily morning and evening for a total of 2000 mg/m^2/day on days 1 to 14 of each cycle).

Patients who withdraw from the treatment or have progressive disease will undergo the End of Treatment (EoT) assessments as planned in the [Schedule of Study Procedures](#).

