## 12. Secondary Endpoint Analysis

After 24 PFS events have been realized, the final analysis of PFS will be performed, which will also include an OS interim superiority analyses. A failure to meet statistical criterion for PFS will not prevent the final assessment of survival.

As for the final analysis of PFS, and OS interim analysis, in addition to the efficacy analysis on endpoints PFS and OS, it also includes:

- Summary of treatment discontinuation and study discontinuation;
- Summary of the demographics, baseline disease characteristics;
- Summary of study treatment exposure;
- Summary and analysis of other efficacy endpoints including TTP, DCR, ORR, DOR, CTS;
- Overview summary of TEAEs, summaries of all TEAEs by CTCAE grade, treatment-related TEAEs, TEAEs leading to treatment discontinuation, Injection site reaction TEAEs, serious TEAEs and TEAEs leading to death;
- Summary of local laboratory tests, ECG tests, LVEF and ECOG performance grade;
- Summary of AUC and time-adjusted AUC for Her-2-specific antibody and correlation of the Her-2-specific antibody with change in tumor size, PFS and OS;

The same analysis methods will be used as full analysis described in previous sections of this SAP.

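### SAP 8.1 allows OS to be censored at the data cutoff without proof that the patient was alive then: a minor, conditional flaw in the primary-endpoint rule that is cheap to remove

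*SAP*

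**What the plan says.** SAP 8.1 defines OS from randomisation to death from any cause. Patients who have not died are censored at the last known alive date, "or the data cutoff date for final analysis if the last known alive date is not available yet". The formula that follows carries both dates: "OS time will be calculated as Date of death (or date of last known alive/cutoff date) minus Randomization date + 1". The visible text does not say which records establish the last known alive date, or that a patient must be confirmed alive before the cutoff date is used.

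Other places that bear on the rule:

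- **Other endpoints.** SAP Table 8-1 (PFS), Table 8-2 (TTP) and section 8.2.5 (DOR) censor at a dated event or record: an assessment, randomisation, first response or, in some TTP rows, death. None falls back to the cutoff.
- **Exposure.** For patients still on treatment, SAP 7.3.1 takes the earlier of the cutoff and the latest date recorded on the dosing pages.
- **First contact.** SAP 3.1 states: "Treatment for both groups will begin at the Baseline/Day 0 visit". Randomisation is at the same visit.
- **Withdrawal.** Protocol 8.12 ends survival collection at death, withdrawal or end of trial. Under Protocol 6.5.3, withdrawal of consent for future information stops further collection, but "The Sponsor may retain and continue to use any data collected before such withdrawal of consent".
- **Interim.** SAP 12 describes the final PFS analysis, "which will also include an OS interim superiority analyses", and adds: "The same analysis methods will be used as full analysis described in previous sections of this SAP".

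**The concern.** Censoring at a date for which there is no evidence of life credits the patient with survival time that nobody observed. If the patient was lost earlier, that time enters the risk sets of the patient's arm and lowers its estimated death rate.

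The main clause of SAP 8.1 avoids this, but the fallback does not. It is also the only visible censoring rule in the SAP that moves forward to the cutoff instead of back to a dated record, and it belongs to the primary endpoint. SAP section 1 plans the OS analysis at 24 deaths and section 3.1 plans 36 patients, so about 36 − 24 = 12 patients are censored and each one carries weight.

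Whether the clause does anything depends on how a programmer reads the condition that the date is not available yet.

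**Working it through.** The plan gives no figure to reproduce here. The check asks whom the clause can reach, and how large the effect would be.

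**Step 1: three readings of the condition**

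| Source of the last known alive date | Patients reached by the fallback | Effect on HR |
|---|---|---|
| Any study record | None, because each has a Day 0 record | 0 |
| Any record, but the latest entry is pending for patients still attending | Patients alive and in contact shortly before cutoff | Ratio of HRs 1.000 (assumed last contact 0 to 1.4 months before cutoff) |
| Survival follow-up form only | Anyone who left before a first form entry | See step 3 |

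The third reading is an assumption. What makes it conceivable is that Protocol Table 3 and SAP Appendix 1 place the survival row only at the post-treatment follow-up visit. Neither document says that the date is taken from that form alone.

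**Step 2: inputs for an illustration of the third reading**

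- 36 patients, 1:1, so 18 per arm (SAP 3.1 and 4.4).
- Cutoff at the 24th death (SAP 1).
- Accrual over 22 months (SAP 3.1), taken as uniform (assumption).
- Exponential survival (assumption). The control median of 11.1 months is the chemotherapy-alone median of the phase 3 trastuzumab trial cited in Protocol 1.2, used as an assumption.
- One affected patient, alive when lost, at a time uniform over Days 0 to 175 (assumption). The window cannot be derived from the visit schedule. Under Protocol 6.4.13 the end-of-treatment visit is triggered by confirmed progression or withdrawal, and "the EoT visit will be conducted at least 28 Days (+/- 7) after last dose of study medication", so 28 days is a floor apart from the visit window.

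**Step 3: results**

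Each simulated trial was analysed twice by Cox regression, once censoring the lost patient at last contact and once at cutoff. The ratio is cutoff-rule HR divided by last-contact HR, averaged on the log scale over 6,000 trials. The Monte Carlo standard error of the log ratio is at most 0.001.

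| True HR | Lost patient in vaccine arm | Lost patient in control arm | One in each arm |
|---|---|---|---|
| 1.00 | 0.920 | 1.089 | 1.001 |
| 0.82 (11.1/13.5, assumed) | 0.925 | 1.095 | 1.014 |

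At true HR 1 that is 1 − 0.920 = 8.0% down or 1.089 − 1 = 8.9% up. The lost patient is credited with about 17 unobserved months on average.

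**Step 4: hand check at true HR 1**

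- Monthly hazard = ln 2 / 11.1 = 0.0624.
- Deaths per arm are about 24/2 = 12, so person-time per arm is about 12/0.0624 = 192 patient-months.
- Adding 17 unobserved months to the vaccine arm multiplies the HR by 192/(192 + 17) = 0.92.
- Adding them to control multiplies it by (192 + 17)/192 = 1.09.

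Both agree with the simulation.

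**The case against.** The strongest defence is that the main clause already governs the harmful case. A patient lost early does have a last known alive date: randomisation, first treatment, vital signs and blood sampling all fall on Day 0, and those data stay usable after consent withdrawal. The word *yet* fits a pending entry for someone still in follow-up, and there the effect is negligible. Protocol 6.4.14 allows survival contact by phone, email, medical records or public information. SAP 7.3.1 takes a maximum over several case report pages, which points away from a single-form derivation. A definition may also sit in text missing from the public version of SAP 4.1, 4.2 or 8.1. The closing line of SAP 8.2.8.3 permits a further survival analysis using vital status collected after cutoff.

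Most of this stands, and it is why the point is minor. It does not rescue the clause, however. If the defence is right, the fallback has little or no work to do and can go. The extra survival analysis is optional and leaves the primary rule unchanged.

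A reader might infer three stronger things that the documents do not support:

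- **That the OS result is biased, or biased towards the vaccine.** No patient without an alive date is shown. The direction depends on the arm, and one patient in each arm nearly cancels. The design is open-label, so unequal loss is possible, but nothing in the documents indicates it.
- **That the visit schedule fixes a period with no survival entry.** It does not, because the end-of-treatment visit waits for progression or withdrawal.
- **That the interim has no usable cutoff.** SAP section 1 names a clinical cutoff at 24 evaluable PFS events, and section 12 runs the OS interim there. That 8.1 names only the final-analysis cutoff is at most a slip of wording.

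**Conclusion.** The wording flaw is real: for the primary endpoint, SAP 8.1 permits censoring at the cutoff without proof of life, and the formula repeats it. Its effect is conditional. It is zero if any study record establishes the alive date, and negligible if only patients still attending are covered. If the date came from the survival form alone, one early-lost patient would move the HR by about 8% down (vaccine arm) or 9% up (control) at true HR 1. That figure rests on assumed exponential survival, an 11.1-month control median, uniform accrual and loss within an assumed first 175 days. It illustrates scale and says nothing about what happened in this trial. The number of such patients is unknown and may be zero. Severity: minor.

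**What to change.** In SAP 8.1, define the censoring date as the latest date on or before the data cutoff at which any study record (visit, dosing, laboratory, imaging, phone or record contact) shows the patient alive, with the randomisation date as the floor. Delete the cutoff-date fallback, or limit it to patients confirmed alive on or after the cutoff, and align the OS formula. For clarity only, add to section 12 that the same rule applies at the OS interim, with the clinical cutoff of 24 PFS events as the cap.

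The cost is a sentence in each section and one derived variable built from dates already collected. Sites need make no extra contact. SAP section 1 already provides for a Final SAP Amendment before the OS database lock.

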## 8.2. Secondary Efficacy Endpoint

### 8.2.1. Progression-free Survival (PFS)

PFS is defined as time in days from the randomization to the date of disease progression or death due to any cause on or prior to the clinical cutoff date, whichever occurred earlier. The disease progression will be defined as the radiological disease progression as assessed by blinded central reviewers. Therefore, duration of PFS in days is defined as the time between the date of randomization and the date of the first occurrence of one of the following events:

- Radiological disease progression per RECIST 1.1 as assessed by the blinded central reviewers, i.e. a tumor response of PD is observed
- Death due to any cause

The calculation of PFS is a two steps process.

- Determination of date of disease progression, which is the date of assessment corresponding to the first date time that overall tumor response is “Progressive Disease” on the Overall Tumor Response-RECIST eCRF
- Calculation of duration from randomization to disease progression, death, or censoring date as described in [Table 8-1](#) as follows. In cases where a patient’s tumor is downstaged to become surgically resectable, this is considered a response to treatment with subsequent surgery being part of the patient’s normal clinical care. Such cases are considered evaluable PFS event at time of confirmed progressive disease.

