**Table 8-1 Censoring Conventions for PFS**

Situation	Date of Progression or Censoring	Outcome
Disease progression, and time interval between progression date and previous tumor assessment date with progression-free response is less than or equal to 98 days	Earliest of: 

• Date of first tumor assessment showing new lesion

• Date of first tumor assessment with overall response of PD

	Event
Disease progression, and time interval between the progression date and the previous tumor assessment date with progression-free response is greater than 98 days.	Latest of: 

• the last progression-free assessment date

• randomization date

	Censored
Death without any post-baseline radiological assessment, and time interval between death	Death date	Event

date and randomization date is less than or equal to 98 days		
Death without any post-baseline radiological assessment, and time interval between death date and randomization date is greater than 98 days	Randomization date	Censored
Death before documented progression, and time interval between death date and previous tumor assessment date with progression-free response is less than or equal to 98 days	Death date	Event
Death before documented progression, and time interval between death date and previous tumor assessment date with progression-free response is greater than 98 days	The last progression-free assessment date	Censored
No death or disease progression, no treatment discontinuation due to symptomatic deterioration, and no subsequent anti-cancer therapy (i.e., systemic anti-cancer therapy, anti-cancer surgery, curative radiotherapy).	Latest of 
 
• the last progression-free assessment date
 
• randomization date
 
	Censored
Subsequent anti-cancer treatment (i.e., systemic anti-cancer therapy, anti-cancer surgery, radiotherapy) started prior to progression	Latest of 
 
• the last progression-free assessment date prior to start of anti-cancer treatment
 
• randomization date
 
	Censored
Treatment discontinuation due to symptomatic deterioration prior to disease progression	Latest of 
 
• the last progression-free assessment date before treatment discontinuation date
 
• randomization date
 
	Censored

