### 8.2.2. Time to Progression (TTP)

The time to progression is defined as the time from randomization to the disease progression on or prior to the clinical cutoff date.

Similar with PFS, the calculation of TTP is a two steps process.

- Determination of date of disease progression, which is the date of assessment corresponding to the first date time that overall tumor response is “Progressive Disease” on the Overall Tumor Response-RECIST eCRF
- Calculation of duration from randomization to disease progression, or censoring date as described in [Table 8-2](#) as follows. In cases where a patient’s tumor is downstaged to become surgically resectable, this is considered a response to treatment with subsequent surgery being part of the patient’s normal clinical care. Such cases are considered evaluable for progression analysis at time of confirmed progressive disease.

[figure not shown]

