B A 1 x 10 mL whole blood sample to assess vaccine-specific cytokine levels and in-vitro inhibition of tumor cell growth will be obtained from each patient at Days 0, 84 then every 84 days and at EoT visit.

C 1 x 10 mL (i.e. 1 tube) whole blood sample for humoral immunity at Baseline, Days 21, 42, 63, 84, 126 then every 42 days and EoT visit and 5 x 8 mL blood samples at Baseline, Days 84 then every 84 days and EoT visit for cellular immunity. To be taken prior to vaccination at Baseline visit.

D Chemotherapy will be administered as a concomitant therapy to all patients as a 21-day regimen consisting of: cisplatin by intravenous administration at 80 mg/m^2 on the first day of each cycle and either 5-FU, 4000 mg/m^2 CIV (administered as 1000 mg/m^2/day as continuous infusion for 96 hours on days 1 to 4 of each cycle) or capecitabine for 14 days at 2000 mg/m^2/day, orally (administered as 1000 mg/m^2 twice daily morning and evening for a total of 2000 mg/m^2/day on days 1 to 14 of each cycle), or capecitabine for 14 days at 2000 mg/m^2/day, orally (administered as 1000 mg/m^2 twice daily morning and evening for a total of 2000 mg/m^2/day on days 1 to 14 of each cycle) and oxaliplatin, by intravenous administration at 130 mg/m^2 on Day 1 of each cycle. Body weight to be measured and body surface area to be calculated based on weight and baseline height at the start of each 21-day chemotherapy cycle. Chemotherapy continues until ceased by the investigator as clinically indicated for the care of the patient. To document compliance while away from the clinic, patients will record capecitabine treatment in a patient diary.

E Radiographic assessment to occur within 14 days prior to Baseline Visit, then at Days 42, 84, 126 every 42 days thereafter. Radiographic assessment continues until disease progression according to RECIST 1.1 response criteria irrespective of whether patient has withdrawn from the study.

F Chemotherapy continues for up to 6 cycles until disease progression or until ceased by the investigator as clinically indicated for the care of the patient, whichever occurs first.

G Radiographic assessment according to RECIST 1.1 response criteria at post-treatment follow-up visit only for patients withdrawn from the study prior to disease progression.

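### SAP text keeps patients resected after downstaging evaluable for PFS and TTP until progression, but Tables 8-1 and 8-2 censor them before the surgery

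*SAP*

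**What the plan says.** **Text.** For a tumor downstaged until it can be resected, SAP 8.2.1 says "this is considered a response to treatment with subsequent surgery being part of the" patient's normal care, and then: "Such cases are considered evaluable PFS event at time of confirmed progressive disease". SAP 8.2.2 has the parallel sentence for TTP: "Such cases are considered evaluable for progression analysis at time of confirmed progressive disease". In both sections this wording sits in the same bullet that sends the analyst to the censoring table.

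**Tables.** Table 8-1 has a row for "Subsequent anti-cancer treatment (i.e., systemic anti-cancer therapy, anti-cancer surgery, radiotherapy) started prior to progression". Its outcome is censored, at the later of randomization and "the last progression-free assessment date prior to start of anti-cancer treatment". Table 8-2 has the same row with the same outcome. Neither table exempts resection after downstaging.

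**The row that competes with it.** Table 8-1 also has a row with outcome Event: "Disease progression, and time interval between progression date and previous tumor assessment date with progression-free response is less than or equal to 98 days". A resected patient who later progresses can meet both rows, and no order of precedence is given.

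**Radiotherapy.** The row for patients without progression or death requires "no subsequent anti-cancer therapy (i.e., systemic anti-cancer therapy, anti-cancer surgery, curative radiotherapy". That row lists only curative radiotherapy, whereas the censoring row lists radiotherapy without qualification.

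**The concern.** The same patient can be programmed in two ways, and the SAP supports each. The patients concerned are not a random subset, because the SAP itself describes the downstaging that leads to surgery as a response to treatment. Censoring at surgery may therefore be informative, and it could differ by arm if downstaging does. SAP 4.4 states that everyone except the central radiography readers is unblinded, so a rule left open could be settled after arm and outcome are known.

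The rule also affects timing. SAP Section 1 triggers the PFS analysis at 24 evaluable PFS events, and whether a resected patient supplies one of them depends on which rule is used.

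The conflict carries into other analyses. SAP 8.2.6 applies the same methods to the investigator assessments, and the clinical-progression sensitivity analysis in 8.2.8.1 reuses Table 8-1. The visible text of 8.2.5 has no censoring for subsequent treatment, so one patient could be an event for duration of response and censored for PFS. None of the visible sensitivity analyses in 8.2.8 varies the handling of surgery.

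**Working it through.** The plan states no figure to reproduce here. The visible text gives no hazard ratio, alpha or power. The check applies the SAP's own rules to invented patients.

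**Inputs from the documents**
- PFS and TTP = analysis date − randomization date + 1 (SAP 8.2.1, 8.2.2).
- Scans: "then at Days 42, 84, 126 every 42 days thereafter" (SAP Appendix 1, footnote E).
- Progression counts as an event only if it falls within 98 days of the previous progression-free scan (Tables 8-1, 8-2).
- 24 evaluable PFS events trigger the analysis (SAP Section 1). There are 36 patients (SAP 3.1), randomized 1:1 (SAP 4.4).

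**Case 1: resection, then progression under regular scanning.** All days are assumed. Progression-free scans on Days 42, 84, 126, 168 and 210; resection Day 100; centrally read progression Day 252.
- Gap to previous scan: 252 − 210 = 42 days, which is within 98.
- Text: event at 252 − 0 + 1 = **253 days** (253/7 = 36.1 weeks).
- Subsequent-treatment row: the last progression-free scan before Day 100 is Day 84, so censored at 84 − 0 + 1 = **85 days** (85/7 = 12.1 weeks).
- The result is the same for TTP, because Table 8-2 has the same two rows.

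**Case 2: as Case 1, but no progression or death, last scan Day 210.**
- Text: censored at 210 + 1 = 211 days.
- Table row: censored at 85 days.
- Status agrees; only the date differs.

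**Case 3: resection Day 100, no scan between Day 84 and progression on Day 420.**
- Gap: 420 − 84 = 336 days, which exceeds 98.
- The more-than-98-days row censors at 85 days even if the surgery is exempt, so the two rules agree.

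**Case 4: death after resection without progression, within 98 days of the last scan.**
- The downstaging sentence names only progression.
- In Table 8-1 the death row gives an event and the subsequent-treatment row gives censoring, so PFS status depends on precedence.
- In Table 8-2 both rows censor, at different dates.

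**Case 5: palliative radiotherapy Day 100, no progression or death, scans as in Case 2.**
- No-event row (only curative radiotherapy excluded): censored at 211 days.
- Censoring row (any radiotherapy): censored at 85 days.
- The status is censored either way.

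**Size.** One Case 1 patient is 1/24 = 4.2% of the planned events. With 1:1 allocation, SE(log HR) ≈ 2/√events. If such events were lost at a fixed cutoff:

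| Events | SE(log HR) |
|---|---|
| 24 | 0.408 |
| 23 | 0.417 |
| 22 | 0.426 |

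The losses of one and two events are assumed. Because the analysis is event-triggered, the rule may instead move the cutoff date.

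**The case against.** The best defense is that there is one rule and a missing footnote. The downstaging sentence is specific, is attached to the instruction to use the table, is repeated for TTP, and calls the surgery normal care, so the surgery would not be subsequent anti-cancer treatment. Other text points the same way. Protocol 2.2 measures PFS to the earliest progression or death, and SAP Section 8 uses all assessments to the cutoff unless otherwise specified.

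This is a plausible account of intent, and it supports the direction of the fix. It does not remove the contradiction. The tables name anti-cancer surgery without qualification, and applying that row as written removes an event that the text requires.

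A reader might infer more than the documents support:
- *That every resected patient changes status.* Cases 2 and 3 show otherwise. A late recurrence after a long scan gap is censored under either rule.
- *That the radiotherapy wording also turns events into censorings.* The row naming curative radiotherapy applies only to patients without progression or death, and both rows censor. The mismatch can move only a censoring date.
- *That a stated share of PFS events is at risk.* The documents give no resection rate, so any such range would rest on an assumed count.
- *That the rule favors one arm.* Response-linked censoring is a reason for care, but no direction is shown.

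It is also fair to say that PFS and TTP are secondary, and that under SAP Section 12 a failed PFS result does not block the final survival assessment.

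**Conclusion.** The contradiction is real, for both PFS and TTP. It reverses event status for a resected patient who later progresses within 98 days of the previous progression-free scan. It also leaves PFS status undetermined for a death after resection that falls within the 98-day limit. For other resected patients it changes at most a censoring date.

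The size is 4.2% of the planned PFS events for each affected patient. How many there are is unknown; there may be none. The 253-day and 85-day figures rest on invented visit dates with scans kept to schedule. The radiotherapy mismatch is a separate and smaller drafting fault.

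The definition and count of OS events are untouched. SAP Section 12 places an interim look at OS at the PFS cutoff, so at most the date of that look could shift. The point should be corrected, but it does not threaten the primary analysis.

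**What to change.** Amend the SAP as follows:

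1. In Tables 8-1 and 8-2, exempt resection after downstaging, as described in 8.2.1 and 8.2.2, from the subsequent anti-cancer treatment row.
2. State the order of precedence between rows in both tables, including for death after surgery.
3. In Table 8-1, follow exempted patients to centrally read progression or death under the existing 98-day rules. In Table 8-2, follow them to centrally read progression, with deaths censored as that table already specifies. One shared phrase covering progression or death would conflict with Table 8-2.
4. Use a single definition of radiotherapy in the no-event row and the censoring row.
5. Define how a resection after downstaging is identified, and make that identification without reference to outcome. The visible text has no definition or data field for it.
6. Run censoring at surgery as a sensitivity analysis.

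If PFS has already been analyzed, state which rule was used and report both. SAP Section 1 provides for a Final SAP Amendment for significant changes after the PFS analysis.

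The cost is SAP wording, one flag per resected patient and one extra run. Scans to progression, concomitant procedures and post-treatment anti-cancer therapy are already scheduled for collection.
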